The purpose of this study is twofold: (1) to assess the impact a mobile health tool may have on reducing alcohol use and improving quality of life for patients with moderate to high risk drinking patterns and/or mild to moderate alcohol use disorder; and (2) describe how mobile health technology designed to support alcohol use reduction may be effectively integrated into primary care.

The primary aim of this study is to assess the impact on risky drinking patterns and quality of life for patients with risky drinking patterns or mild to moderate alcohol use disorder among patients who self-refer to our study from a primary healthcare system. Patients in the trial will be given versions of an evidence-based mobile-health (mHealth) system (A-CHESS) that is delivered using different implementation strategies according to study group. The original A-CHESS is an evidence-based, smartphone-delivered system characterized by the essential elements of relapse prevention: long duration,^{1,2} assertive outreach,³ monitoring,⁴⁻⁶ prompts,⁷⁻⁹ case management,¹⁰⁻¹² and peer¹³⁻¹⁵ and family¹⁶⁻¹⁸ support that was tested among patients exiting 90-day residential treatment for severe alcohol use disorder. A-CHESS has more than 18 services designed to improve social relatedness (e.g., online peer discussions), coping competence (e.g., guided relaxation and other interventions), and intrinsic motivation (e.g., reminders of why a patient wants and needs to control his or her drinking).

The version of A-CHESS to be tested in this trial maintains its core components but is modified to be appropriate for a self-referred study population in a primary healthcare system who are likely to represent a broad spectrum of patients who use alcohol. We have named this modified version of A-CHESS “Tula,” from the Sanskrit word for balance. We propose to randomly assign 546 patients who self-report moderate- to high-risk drinking patterns from UW Health clinics to one of 3 groups: 1). A self-monitoring group that receives information on alcohol, 2). A peer-supported group that uses the Tula system independently of the health system, or 3). A version of the Tula system that is clinically integrated in the health system.

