2.0 STUDY OBJECTIVES

This project proposes a hybrid type II effectiveness/implementation trial that will test the effect on risky drinking patterns and quality of life associated with patient use of an mHealth system under a variety of implementation

Primary Aim:

Detect the effectiveness of interventions by assessing the difference in self-reported risky drinking patterns and quality of life between subjects in the three study groups (self-monitoring, peer-supported, and clinically integrated groups).

Secondary Aims:

Because the study is designed to investigate both the effectiveness of Tula in primary care and the comparative effectiveness of different implementation strategies, the following secondary goals complement study's primary aims:

- Understand the significance clinician monitoring has on alcohol use interventions and patient outcomes.
- Calculate the costs of health system use for each group.
- Develop an mHealth reimbursement strategy prototype using CMS billing codes in the clinically integrated group.
- Understand the degree to which sex moderates the intervention outcomes among Tula users.
- Understand the degree to which patient competence, relatedness, and autonomous motivation (three tenets of self-determination theory) mediate the intervention effect in the Tula groups.
- Assess the dose/response relationship between Tula use and degrees of outcomes
- Understand the impact clinician monitoring has on AUD treatment.
- Qualitatively assesses clinician engagement and clinic needs to further refine Tula and its associated integration for future implementation and dissemination.

Sub-aim:

- Understand the relationship between pain and alcohol consumption after the 3-month active intervention.

Study Coordination

The Implementation Science and Engineering Lab is the coordinating site for this study. The UW study coordinator will oversee all activities at participating UW Health recruitment sites. Activities include:

- developing site-specific recruitment and data collection processes that meet study objectives;
- training the health coaches on protocol procedures prior to the start of recruitment and continuous monitoring to assure compliance with the protocol and human subjects regulation;
- communicating with site staff via regular conference calls to monitor progress, inform of protocol

Protocol

HS IRB #2019-0337
Version 5. 10/17/19
Version 6. 04/07/20
Version 7. 10/09/20
Version 8. 01/26/21
Version 9. 08/18/21

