8.0 STATISTICAL CONSIDERATIONS

Analyses will assess the effectiveness between the three groups longitudinally on the primary and secondary outcomes.

Descriptive analyses. The research team will use descriptive statistics for all demographic and clinical variables across all three arms. To assess the impact of chance baseline imbalances between arms on intervention effect estimates, variables with noticeable differences will be included as covariates in a sensitivity analysis.

Intervention analyses. The analysis assesses direct treatment effects on patient outcomes over time over the 12-month study period. The research team will construct a longitudinal model of our outcome measures at 0, 1, 2, 3, 4, 5, 6, 7, 8, 9, 10, 11, and 12 months after randomization. The stratification variables will be by clinic, biological sex, and alcohol severity. They will be included as factors in the model and the baseline values of patient outcomes will be included as covariates, with a separate model for each primary outcome (risky drinking patterns, quality of life, and cost). This longitudinal analysis is complicated by the dependence among successive observations made on the same individual. Since complete control of measurement is not possible, there may be incomplete data from individual subjects. Therefore we will conduct a mixed-model analysis of repeated measures based on the general linear model with assessment of various covariance structures (compound symmetric, autoregressive order one, and unstructured). Covariance structure selection will be based on Akaike's information criterion and Schwarz's Bayesian criterion.^{46, 47} Pairwise comparisons between treatment groups and specific treatment time contrasts in the mixed model will be conducted to respond to between-group effects and time-based effects. To address issues of incomplete data we plan to estimate treatment effects according to 4 approaches: intention-to-treat, as-treated, per-protocol, and complier-average causal effect. Missing data patterns will be established from the longitudinal data and will be used to adjust the longitudinal intervention analysis according to pattern-mixture modeling.⁶⁹

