Power. Power calculations are based on the previous randomized clinical trial of the platform.⁷¹ The study is powered to detect a difference between groups in risky drinking episodes across the 12-month intervention period. Based on the attrition rate in the previous randomized clinical trial of Tula, we assume an attrition rate of 23% over the course of the study. To detect an effect size of Cohen's $d=0.23$ the research team will recruit 182 patients per group (546 patients total) to have sufficient power ($1-\beta=0.8$, multiple comparison adjusted $\alpha=0.0167$, two-tailed). This would be a difference of 1.37 risky drinking episodes per month.

Quantitative data collection. The data collected in will come from multiple sources (see Table 1). Data collected from patient surveys will be collected by the Tula system and securely stored on CHESS servers. All log files will be stored on the CHESS server to be used to assess Tula use.

Qualitative data collection. This project will make use of clinician interviews to better understand the effect of Tula in the primary care setting. The interview will occur at intervention month 36 and take place at the clinicians' primary care clinic. Qualitative researchers will ask clinicians to talk about their experiences with Tula to refine the system for future use in primary care.

Qualitative data analysis. Content analysis will describe how Tula use can improve patient outcomes; identify potential improvements in Tula; and identify how qualitative data can supplement the quantitative analysis. A qualitative researcher will construct a coding scheme to assess the ideas of the study in order to capture references to a concept. The analyses will help the research team refine Tula for future dissemination by determining the individual and organizational conditions necessary to promote effectiveness.

Protocol

HS IRB #2019-0337
Version 5. 10/17/19
Version 6. 04/07/20
Version 7. 10/09/20
Version 8. 01/26/21
Version 9. 08/18/21
Version 10. 07/13/23

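### Section 8.0 makes cost a primary outcome while section 2.0 makes it secondary, and with no rule across outcomes the 0.0167 alpha does not secure 5% overall

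*Combined protocol and SAP*

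**What the plan says.** The purpose statement at the front says: "The primary aim of this study is to assess the impact on risky drinking patterns and quality of life". Section 2.0 (Primary Aim) agrees and describes "assessing the difference in self-reported risky drinking patterns and quality of life between subjects in the three study groups". Under Secondary Aims the same section lists "Calculate the costs of health system use for each group".

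Section 8.0 (Intervention analyses) gives a longer list. It plans the longitudinal analysis "with a separate model for each primary outcome (risky drinking patterns, quality of life, and cost", and then: "Pairwise comparisons between treatment groups and specific treatment time contrasts in the mixed model will be conducted". It names four approaches to estimating the effect, intention-to-treat first, and does not say which is primary.

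Section 8.0 (Power) rests on one outcome: "The study is powered to detect a difference between groups in risky drinking episodes across the 12-month intervention period". The alpha there is 0.0167, two-tailed, described only as "multiple comparison adjusted". The target is given as: "This would be a difference of 1.37 risky drinking episodes per month".

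No section gives a testing order, an any-or-all success rule, or a division of alpha across outcomes.

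**The concern.** Current text gives two lists of primary outcomes. Three group pairs make six primary comparisons on the section 2.0 list and nine on the section 8.0 list. An alpha of 0.05/3 pays for three. Whether that matters depends on how the outcomes combine, and the plan is silent on this. If any one success counts, the false-positive risk exceeds 5%. If all must succeed, the risk is controlled but the stated 80% power no longer describes the chance of success. If only risky drinking counts, both figures can stand.

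Two further openings widen the choice. The outcome is called patterns in the aims and episodes in the power paragraph, with no threshold and no rule for scaling a 7-day follow-back (section 6.0) to a month. Quality of life is PROMIS Global Health with no score named, although the title of the cited development paper refers to physical and mental summary scores. As written, a win on quality of life or cost alone could not be shown to be the planned result.

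**Working it through.** **Inputs.** Three groups at 1:1:1 (section 7.0), so three pairs. Alpha 0.0167 two-tailed, power 0.80, d = 0.23, attrition 23%, 182 per group (section 8.0, Power). Two primary outcomes (section 2.0) or three (section 8.0).

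**Assumptions not in the documents.** Overall alpha 5%; one contrast per pair on each outcome; between-outcome correlation from 0 to 0.95; where power is combined, each outcome alone has 80%.

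**The plan's alpha.** 0.05/3 = 0.01667, which rounds to 0.0167; critical value |z| > 2.394. The Bonferroni bound at 0.05/3 per test is 3 × 0.01667 = 5% for three tests, 6 × 0.01667 = 10% for six and 9 × 0.01667 = 15% for nine.

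**Any outcome counts.** Three arms compared pairwise, known variance, no true differences, 6,000,000 simulated trials. Chance of at least one false positive:

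| Primary outcomes | corr. 0 | 0.5 | 0.8 | 0.95 |
|---|---|---|---|---|
| 1 | 4.4% | – | – | – |
| 2 | 8.6% | 8.1% | 7.0% | 5.8% |
| 3 | 12.6% | 11.3% | 9.0% | 6.7% |

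**All outcomes must succeed.** A false claim for a pair requires a false rejection on at least one outcome where the pair is truly equal, so its probability is at most 0.01667. Over three pairs the bound is 5%, however many outcomes there are. With three outcomes, if each pair is truly equal on a different outcome and far apart on the other two, error is 1 − (1 − 0.0167)³ = 4.9% at correlation 0. Power for a pair at correlation 0 is 0.8² = 64.0% (two outcomes) or 0.8³ = 51.2% (three). At correlation 0.5, 0.8 and 0.95 it is 68.7%, 72.9% and 76.5% for two, and 61.1%, 68.7% and 74.5% for three.

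**Ordered rule within each pair** (risky drinking at 0.0167, then one quality-of-life score at 0.0167 only if the first is significant). Bound 3 × 0.01667 = 5%. Over 4,000,000 simulated trials with quality of life null and correlation 0, error is 4.4% if drinking is equal in all arms, 4.8% if equal in two and very different in the third, and 4.4% if different in all. One score must be named: two scores each at 0.0167 behind the gate would give 7.0–8.6% (score correlation 0.8 to 0, drinking different in all arms).

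**Equal split over six tests.** 0.05/6 = 0.0083, critical value 2.638. Power at the planned size is Φ(2.394 + 0.842 − 2.638) = Φ(0.598) = 72.5%. Restoring 80% multiplies the size by ((2.638 + 0.842)/(2.394 + 0.842))² ≈ 1.157, so 182 becomes 211 per group, 633 in all.

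**Limit of the check.** The 182 per group was not reproduced. The two-sample formula gives 2 × (3.236/0.23)² ≈ 396 evaluable, and 396/0.77 ≈ 515 enrolled, per group. An unstated repeated-measures assumption could close the gap, for example 13 measures at within-person correlation 0.30: variance factor (1 + 12 × 0.30)/13 = 0.354, and 396 × 0.354 ≈ 140, or 182 × 0.77. The error rates above do not depend on 182; the power figures take 182 and 80% as given.

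**The case against.** The strongest reply is that the power paragraph settles the matter: it singles out risky drinking and sets an adjusted alpha, so risky drinking decides and error is 4.4%. That is a fair inference, and the figure is right if there is one prespecified contrast per pair. But powering a study on an outcome does not say that it alone decides, and section 8.0 still labels three outcomes primary.

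A second reply is that co-primary outcomes need no split of alpha. That holds when all must succeed. The plan does not say so, and its 80% would then be too high.

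A reader might go further and infer that 0.0167 cannot cover both the pairs and the outcomes under any rule. The documents do not support that: an all-must-succeed rule and an ordered rule each hold 5% at 0.0167. What is missing is the rule.

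Three other strong readings also fail. The four estimation approaches are introduced to deal with incomplete data, so they need not be four rival deciding analyses, though naming the primary one is still needed. The drinking days in the cost-effectiveness ratio are that ratio's unit, not a competing primary variable. The 7-day follow-back is the instrument that Table 1 already assigns to risky drinking patterns. The real gap is patterns against episodes, with threshold and scaling undefined.

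Finally, putting quality of life behind risky drinking is partly a preference, since the primary aim names the two together. Only the power paragraph supports that order, so an equal-footing alternative is offered.

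**Conclusion.** The point holds. The primary list in section 8.0 conflicts with the purpose statement and section 2.0, and 0.0167 does not hold 5% over six or nine tests unless an ordered or all-must-succeed rule is stated. Under an any-success rule the excess is modest to substantial and shrinks as the outcomes become more correlated; under an all-must-succeed rule the loss is in power instead. Reading 0.0167 as covering three pairs on one outcome is the natural inference, but it remains one: the text would also fit three outcomes, leaving the pairs uncovered. It would be wrong to report that this trial's error rate is inflated, since that presumes a decision rule the documents never state. This should be fixed, and the repair is cheap.

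**What to change.** By dated amendment:

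1. Reconcile section 8.0 with section 2.0 by making cost secondary. Keep its modelled three-group comparison as a secondary analysis, because the cost-effectiveness ratio in section 8.0 compares only the clinically integrated and peer-supported groups.
2. State that risky drinking episodes decide the trial, by intention-to-treat in all randomised patients, with one prespecified across-follow-up contrast per pair. The other approaches and time contrasts are supportive.
3. Keep for each outcome the assessment times its own model uses. Reconcile the monthly list in section 8.0 with the quarterly schedule in Table 1, in line with whatever repeated-measures assumption gave 182. Do not confine drinking to the quality-of-life times: if 182 rests on 13 measures at correlation 0.30, using four gives a variance factor of (1 + 3 × 0.30)/4 = 0.475, and power drops to Φ(3.236 × √(0.354/0.475) − 2.394), about 65%.
4. Define the episode (threshold, and scaling from 7 days to a month) and name one PROMIS Global Health score.
5. For each pair, test risky drinking at 0.0167, then that score at 0.0167 only if risky drinking is significant for that pair.

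Alternative: keep the two outcomes on equal footing at 0.05/6 per test and restate power as about 72%.

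The cost of the ordered version: quality of life can be claimed for a pair only after risky drinking, a 64.0–76.5% chance if both effects have 80% power, and cost loses its primary label. It needs no new data, and the power calculation keeps its alpha.

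On timing, section 4.0 indicates that some participants have completed 12 months, and section 7.0 gives the research team access to all groups' data. That does not show that outcomes have been compared by group. If they have, the amendment should say so and label the order post hoc.

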5.0 INTERVENTION PLAN

All patients enrolled in the study will participate in a 3-month intervention period followed by a 9-month follow-up period, for a total of 12 months. Patients are allowed to continue using Tula after the 12-month period, but will not be asked survey questions after 12 months. Please note that Tula is not a treatment—it is a resource used to help patients reduce their drinking.

All patient subjects will undergo a 72-hour run-in period when they will have access to the basic version of Tula. During this period, potential subjects will be asked to complete the Quick Start checklist items within the 72 hours. The checklist tasks are completing the baseline survey; setting goals for the 90-day active intervention period related to drinking and, optionally, to other aspects of health (e.g., sleep, exercise); completing the first weekly survey; and completing a survey called What Matters to Me, which helps patients think about their current health status and what they would like to change. After 72 hours, patient subjects who complete these tasks will be randomized to one of three groups and receive the appropriate access to Tula features.

Patients in all three groups—regardless of randomization group—will have access to the same static content on Tula, which is described in Section 1, Background and Significance. In addition, patients in all three groups will be asked to complete (1) a weekly survey during the active intervention period and, optionally, to revise the goals they set during the run-in period and (2) quarterly surveys at month 3, 6, 9, and 12. Subjects are free not to answer any survey questions.

Self-monitoring (control) group. Patients of this group will continue receiving regular care from their physician with no interference from the two experimental groups. No data will be shared with other participants. Only the research team will have access to subject data for evaluation purposes.

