Clinically integrated group. In addition to receiving the same static content available to all patients, patients in the clinically integrated group will also have access to a discussion group with others in the group (like the peer-supported group described above) and access to a health coach from the UW Health Wellness Center. Health Coaching at UW Health's Center for Wellness at the American Center is provided by a Certified Wellcoach, either in-person at the American Center or over the phone. Health Coaching sessions are not scheduled via Health Link: Health Coaches directly and independently manage their own client calendars. Patients schedule a session directly with the Health Coach via phone or email. When the Health Coach sees a client for more than one session, they schedule the first session via phone or email, then set up subsequent sessions during the first session. Standard clinical Health Coach appointments are not documented in any way in Health Link, nor will they be for this study; as an out-of-pocket, open-to-the-public service, The Center for Wellness uses an independent third-party system, ActiveNet, for any billing needs.

Patients will be encouraged to participate in up to three in-person or phone visits with the health coach at the beginning, middle, and end of the active 90-day implementation period, with the first visit lasting between 60 and 90 minutes and the other two lasting between 20 and 45 minutes. The health coach will also function as the moderator of the discussion group, as the peer mentor does in the peer-supported group.

Patients will have the option to share selected Tula data with the health coach through a dashboard. When a patient in this group completes a survey, they will be presented with a question: "Do you want to share your responses with the health coach? Yes/No." If the subject responds "yes," their survey responses will populate a dashboard that contains data on drinking days / drinks per day and other data reported via the weekly survey. The health coach will have the option to view the data in the dashboard. Data in the dashboard will not be placed in the patient subject's electronic medical record. However, if the health coach sees any data that is concerning that would normally prompt follow-up within the scope of their clinical role, the health coach will contact and follow-up with the patient subject if such a situation were to arise.

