Patient and clinician decision making	Value and decision framing survey	Patient/ clinician survey	9	Patient: Pretest, 12 months Clinician: during interview at month 36
Mediators				
Relatedness	CHESS Bonding Scale ^{48,65}	Patient survey	5	
Competence	Perceived Competence Scale	Patient survey	4	0, 3, 6, 9, 12 mo.
Autonomous motivation	TSRQ ⁶⁶	Patient survey	6	
Tula use (patients)	Number of days used, number of pages viewed	Server log files	NA	Continuous
Moderators				
Patient characteristics	Race, ethnicity, gender, age	Patient survey	NA	Pretest

Protocol

HS IRB #2019-0337
Version 5. 10/17/19
Version 6. 04/07/20
Version 7. 10/09/20
Version 8. 01/26/21
Version 9. 08/18/21
Version 10. 07/13/23

All survey data collected through Tula is housed on CHESS servers then exported to the UW sponsored Google Drive folder for statistical analyses.

Screening survey: People interested in participating in the study will be directed to take a Qualtrics screening survey hosted on the Web to determine if they are eligible to participate in the study.

Baseline survey. After patient subjects are enrolled in the study, they will be asked to take a baseline survey consisting of demographic questions, medical service utilization, quality of life, a modified version of the Brief Alcohol Monitor, the CHESS bonding scale, the alcohol competence scale, the TSRQ, and the value of Tula. Data from the screening survey will be used as baseline data for the AUDIT, AUD DSM-5, and timeline follow-back. Two additional questions related to the impact of COVID-19 on participants' physical and mental health will be added to the quality of life measures. These questions will operate on a 5-point Likert scale and will be included across all CHESS studies. (See supporting document "4.6.20 Global Health Scale v1.3_COVID.docx").

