6.0 MEASUREMENT OF EFFECT

All scales have good psychometric properties with similar populations. Listed below are the factors to be measured and measurement instruments.

Intake only. Study staff will confirm patient eligibility via patients' UW Qualtrics screening surveys . Patients report demographics (biological sex, race, ethnicity, age, education).

Protocol
HS IRB #2019-0337
Version 5. 10/17/19
Version 6. 04/07/20
Version 7. 10/09/20
Version 8. 01/26/21
Version 9. 08/18/21
Version 10. 07/13/23

Drinking and quality of life. Patients will be asked to take surveys administered via the Tula app (see Table 1 for frequencies). Patients will be asked to report on their drinking using the 7-day timeline follow-back^{58,59} survey. Patients will also take the PROMIS Global Health⁶⁰ survey (10 items) to assess patient self-reported quality of life and a modified version of the Brief Alcohol Monitor⁶³ survey (10 items) to assess their risk and protection factors for problematic alcohol use. Alcohol use disorder severity (AUD scale,⁶⁴ 11 items; AUDIT, 10 items; 7-day timeline followback, 5 items) will be assessed at baseline and once every 3 months.

Mediators. Self-determination theory constructs will be assessed (see Table 1 for frequencies) via the Tula app as follows:

- Competence – Perceived Competence Scale (4 items)
- Relatedness – CHESS Bonding Scale^{65,66} (5 items)
- Autonomous motivation – revised Treatment Self Regulations Questionnaire⁶⁷ (6 items)

Tula use. Tula use is collected in time-stamped log files and includes when a patient accessed Tula, the services used, duration of service use, pages viewed, messages posted and received, and content of messages. Tula use will be used to measure dose of intervention received for dose/response analyses. Patients will be asked to take a survey about their value of Tula at baseline and 12 months.

Healthcare utilization. Healthcare utilization will be collected from the self-reported medical services utilization form⁶¹ (6 items; see Table 1 for frequency).

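### The missing-data plan gives no role to the weekly drinking reports or app-use logs, so dropout that works differently by arm may bias the contrasts, in either direction

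*Combined protocol and SAP*

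**What the plan says.** Section 8.0 (Intervention analyses) anticipates that "there may be incomplete data from individual subjects. Therefore we will conduct a mixed-model analysis of repeated measures". The model contains clinic, sex and alcohol severity, of which the plan says "They will be included as factors in the model and the baseline values of patient outcomes will be included as covariates". No variable observed after randomisation is named apart from the repeated outcome itself. Two further responses to missing data follow: "To address issues of incomplete data we plan to estimate treatment effects according to 4 approaches" (intention-to-treat, as-treated, per-protocol and complier-average causal effect), and "Missing data patterns will be established from the longitudinal data and will be used to adjust the longitudinal intervention analysis according to pattern-mixture modeling".

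The model is set out on a monthly grid from month 0 to month 12. Table 1 in Section 5.0 schedules the timeline follow-back and PROMIS Global Health at months 0, 3, 6, 9 and 12 only.

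Section 6.0 says of the outcome measures: "Patients will be asked to take surveys administered via the Tula app". Section 5.0 asks all three groups for "a weekly survey during the active intervention period", and Section 4.0 (Remuneration) pays for 12 of them. The description of the coach's dashboard shows what these surveys hold: "data on drinking days / drinks per day and other data reported via the weekly survey". Table 1 also lists Tula use ("Number of days used, number of pages viewed"), taken continuously from server logs. It appears there under mediators, and Section 6.0 assigns it to dose/response analyses. Section 7.0 gives the research team access to all Tula data in every group.

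**The concern.** A mixed model corrects for dropout only so far as dropout is explained by what the model contains. Here a patient who stops opening the app also stops supplying outcomes. If outcomes enter only as Table 1 schedules them, a patient who reports rising drinking for ten weeks and then leaves contributes nothing to the drinking model after baseline. The model then treats that patient as following the average course given baseline.

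The peer mentor and the health coach encourage engagement in two arms. Self-monitoring patients can message only the research coordinator. The kind of patient who leaves could therefore differ by arm. If it does, the comparisons of the supported arms with self-monitoring could be biased, and the trial already holds data that could reduce that bias.

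**Working it through.** **Figures in the plan.** The documents give no figure for dropout bias. The related figures in Section 8.0 (Power) are d = 0.23, 182 per group, 23% attrition overall and a difference of 1.37 episodes per month.
- Implied SD: 1.37/0.23 = 5.96 episodes per month.
- Adjusted alpha: 0.05/3 = 0.0167, which reproduces.
- Sample size by the two-sample formula: 2 × (2.393 + 0.842)²/0.23² = 396 per group, and 396/0.77 = 515 after attrition. The stated 182 does not reproduce without a within-patient correlation that the plan does not give.

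**Which elements use the extra data.**

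| Element | Conditions on | Weekly reports or use logs? |
|---|---|---|
| Mixed model | strata, baseline, repeated outcome | none named |
| Pattern-mixture step | pattern of missingness; identifying restriction not stated | none named |
| Intention-to-treat | defines who is analysed | no |
| As-treated, per-protocol, complier-average | adherence | not for recovering missing outcomes |

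**When bias arises.** Let p be the share missing in an arm. Let δ be how far the model's prediction for those patients falls below their true mean. The arm mean is then too low by pδ, and the contrast is off by p0δ0 − p1δ1.
- Same p and δ in both arms: 0.
- 28% against 18% missing, δ = 0.3 SD in both: 0.28 × 0.3 − 0.18 × 0.3 = 0.03 SD.
- 23% in both, δ = 0.5 SD in one arm only: 0.23 × 0.5 = 0.115 SD, or 0.69 episodes per month. This is an extreme case.

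**Simulation.** All of these inputs are assumptions except the 182 and the 0.23.
- 182 per arm, true difference 0.23 SD.
- Drinking variance: 0.45 stable, 0.30 autoregressive (0.8 per month), and 0.25 noise for a 7-day report (0.25/4 = 0.0625 for a monthly mean of weekly reports).
- Monthly log-odds of leaving are linear in recent drinking, with a slope for each arm.
- About 21% missing, with most dropout before month 3.

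| Slopes (self-monitoring / supported) | Full data | Mixed model, quarterly outcomes | With weekly auxiliaries |
|---|---|---|---|
| 1.0 / 0.3 | 0.233 | 0.211 | 0.223 |
| 0.6 / 0.2 | 0.228 | 0.212 | 0.224 |
| equal | 0.226 | 0.227 | 0.226 |

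First row: bias = 0.233 − 0.211 = 0.022 SD. That is 0.022/0.23 = 9.6% of the target, and 0.022 × 5.96 = 0.13 episodes per month. With auxiliaries, 0.233 − 0.223 = 0.010 remains, so 0.012/0.022 = 55% is removed.

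Variations on the 1.0 / 0.3 case:
- Other dropout intercepts give a bias of 0.018 to 0.024, with 0.004 to 0.010 remaining. The 0.018 and 0.004 come from a run with weekly data for months 1-3 only.
- Slopes reversed: the mixed model gives 0.249, an inflated contrast.
- Months 1-2 of the model filled with monthly means of the weekly reports: 0.223, the same gain as the auxiliaries.
- Standard error: no useful gain from the auxiliaries.

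**A second model.** Here dropout depends on an auxiliary (slope 1) that correlates 0.3 or 0.6 with the visit-specific part of the outcome, and the outcome correlation is 0.5.

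| Dropout | Bias without auxiliary (SD) |
|---|---|
| 23% / 23%, same mechanism | 0 |
| 28% / 18% | 0.006-0.012 |
| 33% / 13% | 0.011-0.023 |
| 23% / 23%, mechanism in one arm only | 0.013-0.025 |
| 23% / 23%, opposite mechanisms | 0.025-0.050 |

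Modelling the auxiliary jointly brings the bias to about zero in every row.

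**The case against.** The strongest reply is the monthly grid in Section 8.0. A model with outcomes at months 1 and 2 needs drinking data for those months, and the weekly surveys are the only described source. If they are meant to fill those months, the mixed model already conditions on them and captures essentially the whole gain shown above. A reader might therefore infer from Table 1 that the weekly data are certainly excluded, and the documents do not support that. Nor do they show that the data are included. Table 1 schedules no drinking measure at months 1-2, and nothing is described that would supply months 4-5, 7-8 or 10-11. Weekly drinking reports would also leave the separate quality-of-life and cost models unaided.

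Second, the mixed model is not the only remedy, and the simulation's comparator has no pattern-mixture step. That is true, and the effect of that step cannot be computed because its identifying restriction is not given. As described, it works from the patterns of missingness and does not use the extra data.

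Third, the gain has limits. Weekly surveys stop at week 12. The simulation assumes they are complete until exit, although patients may skip questions. The use logs, the only added source for later leavers, were not simulated. The bias is also modest, about a quarter of the estimate's standard error (0.022/0.091). These points stand, and they lower the size and certainty of the benefit.

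The statement in Section 5.0 that dashboard information will not serve as study data is no obstacle. It covers what patients share with the coach through the dashboard, not the survey responses themselves.

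**Conclusion.** The gap holds: data that record disengagement are collected in all arms and are given no stated part in handling missing outcomes. The consequence is conditional. If dropout depends on recent drinking differently by arm, bias of roughly 0.02 SD (8-10% of the 0.23 target) is a reasonable working figure under slopes of 1.0 and 0.3 with about 21% missing. About half of it or more can be removed with the weekly reports. Wider assumptions give about 0.006 to 0.05 SD. If the mechanism is the same in all arms, the bias is zero and the auxiliaries do no harm.

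Three stronger readings are not supported:
- **That bias is present.** The documents give 23% attrition overall, with no rate or mechanism by arm. The moderator and coach make a difference plausible, no more.
- **That it must shrink the supported-versus-self-monitoring difference.** Reversing the slopes inflates it.
- **That power falls from 80% to about 70%.** The arithmetic is Φ(3.235 × 0.90 − 2.393) = 0.70. It assumes the direction of bias, and it starts from a power that the stated inputs do not reproduce on their own.

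No precision gain should be claimed either. This is a worthwhile and inexpensive improvement to the plan, held with medium confidence.

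**What to change.** 1. Reconcile the monthly model grid (months 0-12) with the quarterly outcome schedule in Table 1. State whether the weekly drinking reports supply months 1-2, and what, if anything, supplies the other months between quarterly surveys.
2. Keep the planned contrasts, and bring the auxiliaries into the missing-data handling. Multiply impute missing month 3, 6, 9 and 12 outcomes within arm, or fit an equivalent joint model. Include every variable of the analysis model, plus monthly summaries of weekly-survey drinking days and drinks per day for weeks 1-12, and days of Tula use in the preceding month. Monthly summaries are preferable to 24 separate weekly variables (2 × 12) with 182 patients per arm.
3. Keep these post-randomisation variables out of the treatment-effect model.
4. Report the mixed model with and without the auxiliaries. Fix the specification before unblinded analysis, so that the choice is not made after the results are seen.

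The cost is SAP wording, some programming and an imputation step to document. No new data, visits or patients are needed. Weekly reports cannot inform dropout after month 3. There, only the quarterly outcomes and the use logs can help, and the SAP should say so.
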